- Determine if there is a significant difference in opioid requirements in the first 48 hours according to the type of education delivery methods.

Background (Include relevant experience, gaps in current knowledge, preliminary data, etc.):

Despite all the available analgesic, modern devices, and nonpharmacological interventions, pain in the acute post-surgical period remains a prominent issue and effective management has remained elusive with significant gaps in care. Early estimates suggest that anywhere from 50% to 75% of surgical patients experience inadequate pain relief (Huang et al., 2001), often due to delayed intervention (Sinatra, Torres, & Bustos, 2002). A National Survey of patients who had undergone non-specific surgical care demonstrated occurrence of acute pain in 80% of patients and moderate to severe pain in approximately 86% of those who experienced acute pain (Apfelbaum, Chen, Mehta, & Gan, 2003). A 2008 study of 1,490 surgical inpatients, 41% of patients reported severe pain in the first 24 hours after surgery (Sommer, de Rijke, van Kellef, et al., 2008). Watt-Watson, Stevens, Garfunkel, Steiner, & Gallop (2001) found severe pain in 86% of coronary artery bypass patient 24 hours after surgery. A chart review revealed that 80% of these patients experiencing severe pain received <16 mg of morphine over the previous 24 hours and two had no analgesia orders in the medical record (Watt-Watson et al., 2001). Ineffective pain management effects recovery, complications, cost (Gordon, Dahl, & Stevenson, 2000), patient satisfaction (Garinella & Cellini, 2013), length of stay (Joshi, Beck, Emerson, et al., 2014), readmissions (ASA, 2012), quality of life (Ersek, 2001), and chronic postsurgical pain (O'Brien, Pergolizzi, van de Laar, et al, 2103; Barrington, Halaszynski, & Sinatra, 2014).

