
Study Design and Methods

Methods: *Describe, in detail, the research activities that will be conducted under this protocol:*

Variables

The independent variable is the type of patient education deliverable given to the two study arms, group A (experimental group, real-time, interactive, mobile education system) and group B (control group, standard of care). The dependent variables are 1) patient knowledge, 2) patient perceived participation in pain management, 3) high and low pain scores, and 4) total opioid consumption. A simple table of the independent, dependent, and additional variables are presented in Appendix B. A detailed accounting of all data points including variable type, theoretical definitions, and operational definitions can be found in the detailed code book.

Method

Design

This prospective study has been designed as quasi-experimental study. This study design was selected for several reasons. This study seeks to explore both a treatment and control group in efforts to compare outcomes which are dependent on the type of intervention. To control for fidelity of the intervention and avoid cross over, behavior changes from nurses providing the intervention, the intervention the patient receives will be determined by the location they are bedded in hospital. Orthopedic TJA patients are assigned at random and based on bed availability to one of two patient care units. One of the two patient care units will offer standard education the other unit will offer the mobile, iPad based education. The patient care unit to offer the mobile, iPad based education will be selected at random. This study design will help minimize will reduce the risk of selection bias, increase fidelity of the intervention, and increases the probability that the differences demonstrated between the study groups will be attributed to the actual intervention under study.

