Study participants will be assigned into one of two study arms, intervention or control, based on random assignment to the two designated units. At the time of consent, patients will be informed that there are two study arms and that some subjects will receive enhanced pain management education; however, subjects will not explicitly be informed if they are in the intervention or control arm of the study. Participants who have verbally consented will receive a HIPAA authorization form accompanied by a letter reminding them of the study and their consent to participate at the time of the preoperative visit. This typically occurs one to two days before surgery. Participants will be asked to sign the HIPAA authorization form and return the clinical staff. Participants will be provided an extra copy for their records. No Patient data will be collected prior to this. Once HIPAA has been signed participants will complete the intake survey provided with the packet of information.

Researchers are blinded to the study arm the participant was enrolled in until after consent has been obtained, the patient is enrolled in the study, and has been admitted to the hospital and assigned a bed. Once enrolled and consented, bed control will be notified to assign the patient(s) to one of the two designated patient care units with no specific direction offered on which unit the patient(s) should be assigned to. The only direction provided will be to split the patients evenly between the two units. Only ten study arm participants may be enrolled and active at one time. This is limited based on the number of available iPad devices for the purposes of this study.

Study Population

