The target population is adult patients undergoing elective, lower extremity total joint arthroplasty (TJA). Candidates for inclusion are adult patients over the age of 18 years undergoing surgical intervention and inpatient care for one of the following procedures, total hip arthroplasty (THA) (primary, bilateral, and revision) and total knee arthroplasty (TKA) (primary, bilateral, unicompartmental, and revision). Patients must be fluent in the English language. Patients will be excluded if they are undergoing more complex hip and knee procedures such as implant resections with or without spacer placement, liner exchange, or THA or unipolar hip arthroplasty related to repair of hip fracture. Patients will also be excluded if there are preexisting physical or cognitive limitations that would hinder their ability to use the mobile application.

Sample Size

Assuming a moderate effect size 0.50 (Cohen's d), a power of 80% (0.80), and an alpha of 0.05, 64 participants are needed in each study arm (Polit, 2010). Due to limited time scope, a minimum of 150 patients will be approached for potential participation. If time allows and additional subjects are needed to achieve the desired sample size, additional candidates will be approached to reach the recommended total of 128 patients, divided between the two study arms.

Recruitment and Consent

Eligible patients will be identified using surgeon referral and/or electronic surgical listing reports. Enrollment into the study is completely voluntary. Patients will be recruited at the time of perioperative phone consultation with nursing. This consultation occurs approximately two weeks prior to their scheduled surgical procedure. At this time patients will be introduced to the study by the RN or APRN. If the patient expresses interest, verbal consent will be obtained and documented at the time of the call by the IRB approved consent designees. Consent designees will read the consent script and provide any necessary time to answer the patients' questions. At the time of consent, patients will be informed that there are two study arms and that some subjects will receive enhanced pain management education; however, subjects will not explicitly be informed if they are in the intervention or control arm of the study.

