There is a risk for disclosure of personal protected information. The electronic data will be stored on an internal secure server. If transport of electronic data is necessary for any reason an encrypted storage device will be used. Paper and pencil surveys will be stored in a locked cabinet, in a locked and secure office. The researcher and the RN will be responsible to data entry into SPSS. The RN will be trained by the researcher on SPSS data entry. Access to the data will be restricted to only research personnel approved on the IRB application. The RNs will complete the institution's IRB education requirements for staff assisting with research data. Limiting the number of staff involved will reduce the potential for data entry errors.

Setting

The intervention and data collection will be collected on orthopedic patients admitted to two orthopedic inpatient care units who have undergone major joint replacement surgery at a large academic medical center in the upper Midwest. Between the two units there are 50 dedicated orthopedic beds that admit more than 9,000 orthopedic patients annually. Included in the annual orthopedic admits are approximately 4,000 major total joint arthroplasties. Based on historical admission data and patient volumes the desired sample size is feasible. Patients relocated to non-orthopedic units due to high patient census will not be included in the study. The goal is to recruit 20 patients on a weekly basis, ten in each arm of the study. Due to the restricted number of iPads

available, only ten patients may be enrolled in the study arm at any point in time. The total divided sample of 124 patients should be achievable within ten weeks from the start of the study.

Intervention

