Patient demographics and clinical characteristics. Patient demographics and past medical history will be collected as part of the study (Appendix D). Patient demographic variables to be collected include age, race, education level, marital status, and employment status. Specific confounding variables associated with the type of intervention and outcome will be collected including patients' preferred learning style, comfort level with technology, and anxiety. Preferred learning style will be assessed using the three styles of learning reading, seeing, doing, or listening (Bastable, 2008). Comfort level with technology will be assessed using a five-point Likert scale with zero being, "not comfortable at all" and five being "very comfortable." Anxiety associated with anticipated pain will be assessed on ten-point. Relevant past medical and surgical history will also be collected including past major orthopedic surgeries, chronic pain, preoperative use of opioids, and mental health conditions. The patient demographic collection form will be administered using paper and pencil survey. The patient will be given the form when they arrive to the ambulatory orthopedic clinic for their perioperative visit, one to two days prior to their scheduled surgery. It will take participants approximately five minutes to complete the survey.

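### Procedure mix and pre-operative opioid use can differ between the two units, and the plan relies on an unspecified, data-driven baseline check and an unadjusted t-test to deal with it

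*Combined protocol and SAP*

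**What the plan says.** **Eligibility.** Study Population and the Inclusion Criteria admit total hip arthroplasty (primary, bilateral, revision) and "total knee arthroplasty (TKA) (primary, bilateral, unicompartmental, and revision"). Neither chronic pain nor pre-operative opioid use is an exclusion.

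**Assignment.** Under Design, the unit determines the arm: "Orthopedic TJA patients are assigned at random and based on bed availability to one of two patient care units". Bed control is notified of enrolled patients, and "The only direction provided will be to split the patients evenly between the two units". The same section calls the study quasi-experimental. No randomization list, generation method or stratification factor is described.

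**Outcomes affected.** High and low pain scores and total opioid consumption are dependent variables. One aim reads: "Determine if there is a significant difference in opioid requirements in the first 48 hours according to the type of education delivery methods".

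**Data collected.** The intake form, completed one to two days before surgery, records "past major orthopedic surgeries, chronic pain, preoperative use of opioids, and mental health conditions". The chart audit confirms the reported history and adds the surgical procedure and type of regional anesthesia.

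**Analysis.** The Data Analysis Plan will examine baseline differences to find characteristics that may need control. It then names an independent t-test for the group comparison, with a nonparametric fallback if normality fails. Limitations separately commits to accounting for attendance at the pre-operative class. No such commitment is made for procedure or opioid use.

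**The concern.** A head-count rule is satisfied even if one unit receives more bilateral or revision cases, or more patients already taking opioids. Such characteristics may plausibly be related to post-operative opioid consumption and pain scores, so an unadjusted comparison would mix their effect with that of the education.

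How much this matters depends on how beds are filled. Under genuine random assignment, imbalance arises only by chance. The t-test's standard error already allows for it, and the cost is precision. If bed availability is related to the type of case, the imbalance is systematic and the comparison is biased: a difference could appear without an education effect, or a real effect could be hidden. The documents use the word random but describe placement by availability, so the second possibility cannot be excluded.

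The planned baseline check is the only safeguard that could reach these factors. As written, the analyst would decide after seeing the data which characteristics to control and how.

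**Working it through.** **1. The plan's own figure.** Sample Size gives the basis, with the count being per arm: "Assuming a moderate effect size 0.50 (Cohen's d), a power of 80% (0.80), and an alpha of 0.05, 64 participants are needed in each study". A two-sided two-sample t-test (noncentral t) with d = 0.50, alpha 0.05 and power 0.80 needs 63.77, rounded up to 64 per arm, with power 0.801. The figure reproduces. (Setting gives a total of 124 instead of 128. At 62 per arm power is 0.789. That discrepancy is a separate matter; 64 is used below.)

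**2. What is not in the documents.** They give no outcome SD, no prevalence of bilateral, revision or opioid-using patients, and no effect of these factors on the outcomes. The values in steps 3 and 4 are assumptions, shown as ranges.

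**3. Chance imbalance under truly random assignment.** Let p be the share of high-need patients (bilateral, revision or pre-operative opioid users), assumed 0.15-0.35. Let s be how far their mean lies above the others, assumed 1-2 within-class SD.

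- 95% half-width of the between-arm difference in p: h = 1.96 × sqrt(2p(1−p)/64)
- Shift in the outcome, in within-class SD: h × s
- Total SD, in within-class SD units: sqrt(1 + p(1−p)s²)
- Shift in total SD, the scale of d for an unadjusted t-test: h × s / total SD

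| p | s | h (points) | shift, within-class SD | total SD | shift, total SD | share of d = 0.50 |
|---|---|---|---|---|---|---|
| 0.15 | 1 | 12.4 | 0.124 | 1.06 | 0.117 | 23% |
| 0.15 | 2 | 12.4 | 0.247 | 1.23 | 0.201 | 40% |
| 0.25 | 1 | 15.0 | 0.150 | 1.09 | 0.138 | 28% |
| 0.25 | 2 | 15.0 | 0.300 | 1.32 | 0.227 | 45% |
| 0.35 | 1 | 16.5 | 0.165 | 1.11 | 0.149 | 30% |
| 0.35 | 2 | 16.5 | 0.331 | 1.38 | 0.239 | 48% |

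These are the edges of a 95% range centred on zero. They show how much of the outcome noise comes from case mix. They are not an expected bias.

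**4. Systematic imbalance, if bed filling follows case mix.** Bias in SD = (difference in prevalence) × (effect of the factor, assumed 0.5-1.0 SD). Type I error and power come from the noncentral t with 126 degrees of freedom and noncentrality (shift) × sqrt(64/2). For power, the shift is 0.50 minus the bias, that is, a bias working against a true d of 0.50.

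| Imbalance | Bias (SD) | Share of d | Type I error | Power if the bias opposes the effect |
|---|---|---|---|---|
| 10 points | 0.05-0.10 | 10-20% | 0.059-0.087 | 0.71-0.61 |
| 20 points | 0.10-0.20 | 20-40% | 0.087-0.202 | 0.61-0.39 |

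**5. Effect of adjusting.** If pre-specified covariates explain a share R² of the outcome variance, the residual SD is sqrt(1 − R²). With R² assumed at 0.05, 0.10, 0.20 and 0.30, power at 64 per arm is 0.82, 0.84, 0.88 and 0.92, against 0.80 unadjusted. The sample size does not rise. These figures take the covariates as roughly balanced; a large imbalance would give back part of the gain.

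**The case against.** The strongest reply is that the plan already foresees this: the confounders are recorded, procedure and history are checked at chart audit, and baseline differences that need control are to be sought. That stands as mitigation. A reader might infer that any imbalance passes uncorrected into the opioid and pain results; the Data Analysis Plan does not support that reading. It does leave covariates, trigger and model unstated.

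Three other stronger readings also fail.

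- **Size.** Dividing the within-class shifts in the working (0.124 to 0.331) by 0.50 gives about 25% to 66% of the planned effect. This mixes scales, because d in an unadjusted t-test is in total SDs. On the same assumptions the range is 23-48%.
- **Chance imbalance as bias.** Under random assignment the type I error stays at 5%. Only bed filling related to case mix makes it bias.
- **A known tendency in bed control.** Nothing in the documents says either unit receives more revision, bilateral or opioid-using patients. The concern is that the described procedure does not prevent it.

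Balancing at assignment also has limits. Recruitment and Consent restricts data access to approved research personnel, and bed control is not described as such. Notice to bed control follows enrolment and consent. Verbal consent is given about two weeks before surgery, while the intake form is completed one to two days before, so the opioid answer may not exist when notice is sent.

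**Conclusion.** The concern holds as a weakness in the pre-specified analysis. Eligibility is broad, assignment balances numbers only, and the plan's response is a data-driven check with no named covariates followed by an unadjusted t-test. If assignment is effectively random, the loss is mainly precision: a 95% chance shift of about 0.12-0.24 total SD (23-48% of d = 0.50), for an assumed 15-35% high-need share and 1-2 within-class SD separation. If bed filling is related to case mix, there is bias: with an assumed factor effect of 0.5-1.0 SD, a 20-point imbalance gives a type I error of about 0.09-0.20. The documents do not show which situation applies and give none of these inputs, so the figures illustrate size and do not estimate it.

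**What to change.** **Data Analysis Plan (main change).** For opioid consumption and pain scores, replace the unadjusted t-test with a comparison fixed in advance (ANCOVA/regression, or stratified). Adjust for:

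- joint (hip or knee);
- procedure class (unilateral primary or unicompartmental versus bilateral or revision);
- pre-operative opioid use (yes or no).

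Apply it whether or not a baseline imbalance is seen. State that the nonparametric fallback keeps the same factors, for example as a stratified rank test. The unadjusted t-test can be reported alongside.

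**Design (optional).** Ask bed control to split patients evenly within procedure class, taken from the surgical listing, and accept approximate balance when beds are short. Do not pass the intake-form opioid answer to bed control, because of the data-access limit and the timing of the notice.

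**Cost.** A few sentences in the analysis plan and slightly more analysis work. No new data or patients are needed, since the intake form and chart audit already supply all three factors. The optional step adds one sentence and a class label on the notice. Neither step separates the education effect from a unit effect, because each arm is a single unit; the report should say so.

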The Impact of Mobile Education Delivery on Postoperative Pain Outcomes

Study Protocol

IRB Number: 17-04771

NCT number: NA

8/14/2017

IRB Minimal Risk Protocol Template

Note: If this study establishes a human specimen repository (biobank) for research purposes, do not use this template. Use the Mayo Clinic Human Specimen Repository Protocol Template found on the IRB home page under Forms and Procedures at <http://intranet.mayo.edu/charlie/irb/>

First-time Use: Use this template to describe your study for a new IRB submission.

1. Complete the questions that apply to your study.
2. Save an electronic copy of this protocol for future revisions.
3. When completing your IRBe application, you will be asked to upload this document to the protocol section.

Modification: To modify this document after your study has been approved:

1. Open your study in IRBe. Click on the study 'Documents' tab and select the most recent version of the protocol. Save it to your files.
2. Open the saved document and activate "Track Changes".
3. Revise the protocol template to reflect the modification points , save the template to your files
4. Create an IRBe Modification for the study and upload the revised protocol template.

General Study Information

Principal Investigator: [name]

Study Title: The Impact of Mobile Education Delivery on Postoperative Pain Outcomes

Protocol version number and date: Version #1 May 2, 2017

Research Question and Aims

Hypothesis: It is hypothesized that a real-time, interactive, mobile education system will demonstrate improved pain associated outcomes, and higher patient participation when compared to the current standard education delivery method.

Aims, purpose, or objectives: This study seeks to understand the difference between two different education delivery methodologies and the effect on the postoperative pain experience, including participation in treatment plan, knowledge, pain outcomes, and opioid requirements.

- Evaluate the difference in patients' self-reported pain experience according to the type of education delivery methods.
- Determine if there are significant differences in patients' knowledge of pain, medications, and side effects according to the type of education delivery methods.
- Evaluate the difference in patients' self-reported participation in pain management according to the type of education delivery methods.

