Chart audits. Chart audits of the electronic health record will be conducted after discharge to collect the remaining clinical data. Data to be collected will include total opioid requirements as indicated by the medication administration record; primary surgical procedure as reported in the surgical listing and the operative report; type of regional anesthesia as indicated in the anesthesia record; length of stay; and discharge disposition as reported in the hospital dismissal summary. Additionally, the past medical history will be reviewed to confirm patient reported history of chronic pain, preoperative use of opioids, and mental health conditions. The researcher and a staff RN will conduct these chart audits.

Limitations

The design of this study does present some limitations. Participants in the study group will receive enhanced pain content that is delivered using an alternative method, ultimately testing both the delivery method and the content. The duality of the study intervention is a confounding variable and may make differentiating

the cause of the outcome difficult. Another limitation is that preoperative educational classes are available to patients to attend if they choose. All patients receive the same pamphlets and information in the mail when surgery is scheduled. An in-person didactic class is optional for patients. Some pain education is offered in this class. Currently only 49% of patients attend these classes. It is anticipated that some patients enrolled in the study will have received varying levels of education prior to their hospital admission. This is an antecedent variable that will be collected as part of the chart audit and accounted in the data analysis. The two nursing units involved in the study are located within the same hospital. It is possible that nursing staff from the intervention unit may float to the control unit and educate study patients using content from the expanded education from the intervention on the iPads. Pre-testing knowledge of pain and measured again at the end of the intervention (prepost) using a paired t-test analysis will strengthen the design of the study. Only opioid use for pain control is being measured.

Data Management

Data Collection Procedure

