Account, member, certificate or professional license numbers, health beneficiary numbers		
Vehicle identifiers and serial numbers, including license plate numbers		
Check 'None' when none of the identifiers listed above will be recorded, maintained, or shared during the conduct of this study. (exempt category 4)	 None	 None

Data Analysis

Power analyses and study endpoints are not required for minimal risk research, pilot or feasibility studies.

No statistical information. *If checked, please explain:*

Power Statement: N/A

Data Analysis Plan

The pre-intervention and post-intervention, paper surveys' will be returned to the researcher for data entry and storage. The collected data will be collated and entered by the researcher into SPSS for data analysis. A detailed code book has been developed to include specific information on the type of variable and the theoretical and operational definitions. Data entry will be double-checked for accuracy by one of the staff trained staff RNs participating in data collection and chart audits. Descriptive statistics will be performed on each study variable. Continuous variables, including pain scores, pain knowledge, and opioid requirements, will be reported using a mean and standard deviation. Categorical variables, including patient characteristics and education engagement, will be reported as frequencies and percent occurrence. The data will be examined for any baseline differences between the groups to identify characteristics that may confound results and require control in the analysis. Data will be examined to assure that it meets the assumptions of normality required for parametric analysis. If data does not meet normality assumptions, nonparametric analyses will be used. This study uses a revised adaption of the Patient Pain Questionnaire (PPQ) survey. For this reason, the reliability and validity of the nine knowledge based questions will be evaluated using Cronbach's alpha and factor analysis.

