This study will explore the difference between two types of education delivery methods and the effect on pain scores, participation, knowledge, and opioid requirements. The difference amongst the two study groups will be analyzed using an independent *t*-test. Using the population mean of each group a *t* statistic will be computed. The independent *t*-test was selected because this statistical test is appropriate when there are two groups that are not the same people and are not connected to one another in any other systematic way (Polit, 2010). Additionally, the requirements for the *t*-test fit with the design of the study and variables. The independent variable must be dichotomous nominal level indicating a participants' status in one of the two groups and the dependent variable must maintain the characteristics of interval-scale or ratio (Polit, 2010).

Endpoints

Primary: N/A

Secondary: N/A

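### The sample size of 64 per arm is tied to no outcome, and at least four outcomes are tested with no primary endpoint, multiplicity rule or success rule

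*Combined protocol and SAP*

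**What the plan says.** The Sample Size section takes a Cohen's d of 0.50 and states "a power of 80% (0.80), and an alpha of 0.05, 64 participants are needed in each study arm". It gives no outcome, raw difference, standard deviation or sidedness.

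The Variables section lists the dependent variables as "1) patient knowledge, 2) patient perceived participation in pain management, 3) high and low pain scores, and 4) total opioid consumption", and adds that "operational definitions can be found in the detailed code book"; that code book is not among the documents. The Data Analysis Plan examines "the effect on pain scores, participation, knowledge, and opioid requirements" with an independent t-test between groups, and adds: "If data does not meet normality assumptions, nonparametric analyses will be used". The Limitations section adds a pre–post comparison of knowledge, "using a paired t-test analysis will strengthen the design of the study".

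The hypothesis is directional: the mobile system "will demonstrate improved pain associated outcomes, and higher patient participation when compared to the current standard education delivery method". The Endpoints entries for primary and secondary are both N/A, as is the Power Statement under Data Analysis. The form itself notes there: "Power analyses and study endpoints are not required for minimal risk research, pilot or feasibility studies".

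The target total is 128 under Sample Size and Target accrual, but 124 under Setting.

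**The concern.** An 80% power statement has meaning only for a named outcome, and here the reader cannot tell which one it covers. The only significance level in the documents is the 0.05 in the sample size calculation. Nothing ranks the outcomes, divides that level among them, or says how many must succeed for the hypothesis to be supported.

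With at least four comparisons and no such rule, one chance result in favour of the mobile arm could be reported as support. The candidate outcomes are also loosely defined. Opioid use, for example, covers the first 48 hours in the aims but is a total, with no time window, under Variables and Chart audits. That leaves room to choose after the data are seen.

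**Working it through.** **Inputs from the documents.** d = 0.50, power 0.80, alpha 0.05 and 64 per arm (Sample Size); an even split between units (Study Design and Methods); four outcomes, or five if high and low pain scores are separate (Variables).

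**Assumed.** Each outcome is tested at two-sided 0.05; correlation between outcomes is 0, 0.3 or 0.5; d = 0.5 on each outcome where power is computed. Correlated cases are simulated.

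**1. The plan's own figure.** Two-sample t-test, noncentral t, d = 0.5, 80% power:
- two-sided 0.05: 63.77, so 64 per arm (power at 64 = 80.1%)
- one-sided 0.05: 50.15, so 51 per arm

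Only the two-sided test gives 64, which is why two-sided is inferred.

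**2. Any one favourable result counts as support.** No true effects; each two-sided test has a 2.5% chance of falsely favouring the mobile arm. Under independence the rates are 1 − 0.975^k (favourable) and 1 − 0.95^k (either direction).

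| Outcomes | Direction | Correlation 0 | 0.3 | 0.5 |
|---|---|---|---|---|
| 4 | favourable | 9.6% | 8.8% | 7.8% |
| 5 | favourable | 11.9% | 10.5% | 9.2% |
| 4 | either | 18.5% | 17.4% | 15.6% |
| 5 | either | 22.6% | 20.9% | 18.3% |

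The favourable rate is 7.8/2.5 = 3.1 to 11.9/2.5 = 4.8 times that of a single test.

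**3. A pain outcome and participation must both succeed.** Suppose pain has no true effect and participation truly has d = 0.5.
- Pain outcome fixed in advance: 0.025 × 0.8015 = 2.0% under independence, and never above 2.5%, because the pain test alone caps it.
- Any of three pain measures may serve (high score, low score, opioid use): (1 − 0.975^3) × 0.8015 = 0.0731 × 0.8015 = 5.9% under independence, and about 6–6.5% at correlations 0.3–0.5.
- Power for both of two fixed outcomes, each with d = 0.5: 0.8015² = 64% under independence, 67% at 0.3 and 69% at 0.5.

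**4. What 64 per arm supports under Holm.** Power for one outcome at the strictest step:
- three outcomes (0.05/3): 65.6%
- four (0.0125): 61.6%
- five (0.01): 58.5%

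If every outcome truly has d = 0.5, average Holm power per outcome is higher, about 71–73% (four) or 69–70% (five). Restoring 80% at the strictest step needs 90.8, so 91 per arm (four), or 95.1, so 96 (five).

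**5. A primary at 0.05 plus Holm on three secondaries, with no gate.** Chance of any false positive in either direction under independence: 1 − 0.95 × (1 − 0.05/3)^3 = 1 − 0.95 × 0.9508 = 9.7%. At correlation 0.5 it is about 8.5%. Naming a primary without a gate or a label therefore does not hold study-wide error at 5%.

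**6. The totals.** 124/2 = 62 per arm gives 78.9% power against 80.1% at 64. If 128 counts enrolled patients, 5% loss leaves 64 × 0.95 = 60.8 per arm (78.1%) and 10% loss leaves 57.6 (75.8%). The loss rates are assumptions; the documents give none.

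**The case against.** The strongest defence is that this is a minimal-risk, quasi-experimental study on a form that waives endpoints and power analyses. The protocol says in its Design section and Data Analysis Plan that it will *explore* differences, and it lists four separate aims. One test per aim at 0.05 is a defensible convention for such a study. This explains the N/A entries: leaving them so does not breach the form. It does not close the gap, because the protocol went further than the form asked. It states a directional hypothesis and a power-based sample size, and nowhere says that the results will not be used to declare that hypothesis supported.

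A second objection is that the error rates in step 2 depend on a success rule that the documents do not state. That is right, and the rates are conditional on it. The hypothesis joins pain outcomes and participation with *and*, so a reader might infer that both must succeed and that error is not inflated. The text does not secure this, since the pain outcomes are plural and unspecified; step 3 shows that the protection holds only if the pain outcome is fixed in advance.

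A reader might also infer that the sample size is wrong and that 91 or 96 per arm are required. The documents do not support that. Those sizes apply only if all outcomes are confirmatory and 80% power is wanted at the strictest Holm step.

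**Conclusion.** The gap is real and should be closed before outcome data are seen. It concerns error control and interpretation; the arithmetic behind 64 per arm is sound. Without a primary outcome or a success rule, the stated 80% power belongs to no particular claim.

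If any one favourable result is taken as support, the false favourable rate is about 8–12% against 2.5%, and the rate in either direction about 16–23%. If two fixed outcomes must both succeed, error is contained but power is about 64–69%.

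These figures rest on testing each outcome at two-sided 0.05, which is implied but not stated, and on assumed correlations of 0 to 0.5. Four or five outcomes is a minimum, since the code book is not available and the paired knowledge test comes on top. The 124 and attrition points are minor: 1.3 points of power for the first, and about 2 to 4 points for the second at the assumed loss rates.

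**What to change.** **1. Name a primary outcome.** Before any outcome data are seen, replace N/A with one precisely defined outcome of the sponsor's choosing, tested at two-sided 0.05, and tie the 80% power to it. Test the other outcomes by Holm only if the primary succeeds, or label them, together with the paired knowledge test, as supportive with no confirmatory claim. The size of 64 per arm then stands, provided that d = 0.50 is reasonable for the chosen outcome and the t-test assumptions hold. The cost is wording, a justification of d = 0.50, and less weight on the other outcomes (about 66% power at the strictest Holm step with three, 62% with four, before allowing for the gate).

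Two alternatives are acceptable:
- Keep all outcomes co-equal under Holm and state the power: about 62% (four) or 59% (five) at the strictest step, averaging about 69–73% if all have d = 0.5. Restoring 80% at the strictest step would take 91 or 96 per arm.
- State that all tests are exploratory and that the hypothesis will not be declared supported on them. This costs no patients but gives up the confirmatory claim.

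**2. Minor.** Reconcile 124 under Setting with 128 under Sample Size and Target accrual, or state 79% power for 124.

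**3. Minor.** State that 80% power refers to 64 analysed per arm. If 128 is the number enrolled, state that power is about 78% with 5% loss or 76% with 10% loss (assumed rates). Keeping 64 analysed would need 64/0.95 = 67.4, so 68, or 64/0.90 = 71.1, so 72, enrolled per arm.
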